Leber Hereditary Optical Neuropathy (LHON) is an inherited mitochondrial disease of partial penetrance affecting both genders with predominance in males (~80%). The pathophysiology of LHON mainly affects the retinal ganglion cells (RGCs). The ND4 G11778A mutation is responsible for the majority of cases (~70%). Vision loss classically occurs in a bilateral sequential fashion, the second eye becoming involved after the first one with a median delay of 2 months. GenSight Biologics' strategy to specifically treat LHON is based on a gene therapy approach by the development of GS010. The scientific basis behind this Investigational Medicinal Product consists of rescuing mitochondrial function by reaching the nucleus of the target cell, forming intranuclear episomes that can be read and produce specific mRNA inducing ND4 protein synthesis and targeting of the ND4 protein to the mitochondria. This is expected to significantly improve the respiratory chain function. Preclinical studies performed in rats strongly suggest that GS010 displays a potential to restore wild-type ND4 expression.

Study Treatment: GS010 is a recombinant adeno-associated viral vector serotype 2 (rAAV2/2) containing the wild-type ND4 gene (rAAV2/2-ND4). In this study, subjects will receive a single dose of GS010 via intravitreal (IVT) injection containing 9E10 vg in 90µL balanced salt solution (BSS) plus 0.001% Pluronic F68[®].

Target Population:

The study population will be subjects with LHON due to the G11778A *ND4* mutation who have been affected by vision decline for 180 days or less.

Number of Subjects:

It is planned that approximately 40 subjects will be screened in order to randomize 36 into the study at 7 sites (one each in France, Germany, Italy, and the United Kingdom and 3 in the United States).

Objectives: Primary Objective:

To evaluate the efficacy of GS010 compared with sham at Week 48 in the change from baseline of the Log of the Minimal Angle of Resolution (LogMAR) in subjects affected for 6 months or less by LHON.

Secondary Objectives:

- To evaluate the efficacy of GS010 compared with sham over the follow-up period and at Week 96 in the change from baseline of the LogMAR.
- To verify whether the efficacy at Week 48 and at Week 96 of GS010 compared with sham and measured by the change from baseline in the LogMAR is dependent upon the treatment of the better- or worse-seeing-eye.
- To verify whether the rate of responders at Week 48 and 96 is dependent upon the treatment received and whether the magnitude of the treatment effect is dependent the treatment of the better- or worse-seeing eye at entry.
- To assess the effect of GS010 on parameters measured with high resolution spectral-domain optical coherence tomography (SD-OCT).
- To assess the effect of GS010 on standardized automated visual fields obtained with the Humphrey Visual Field (HVF) Analyzer II.
- To assess the effect of GS010 on contrast sensitivity measured with the Pelli-Robson chart.
- To assess the effect of GS010 on color vision measure with the Farnsworth-Munsell 100 Hue color test.

Study Design:

GS-LHON-CLIN-03A is a Phase III double-masked, sham-controlled, multicenter, multi-country study. Recruitment is competitive.

Both eyes will receive standard antiseptic preparation, administration of topical local ocular anesthetic agents and will undergo pupillary dilation. Administration of an intra-ocular pressure lowering agent will precede treatment. GS010 will be administered once during the study via a single IVT injection. Sham IVT injection will be performed by applying pressure to the eye at the location of a typical procedure using the blunt end of a syringe without a needle.

The right eye of each subject will be randomly allocated to receive either GS010 or sham treatment in a 1:1 allocation ratio. The fellow (left) eye will receive the treatment not allocated to the right eye. Therefore, each

subject will receive GS010 in one eye and sham treatment in the fellow eye.

Right eye - GS010 / Left eye - SHAM Right eye - SHAM / Left eye - GS010 Screening Randomization visit W0 W48 W96

An algorithm with a testing hierarchy will be employed to determine the better- and worse-seeing eye of each subject prior to randomization. The randomization will be based on the right and left eye, because if the right eye is treated the left eye will receive sham and vice versa the treatment groups will be automatically balanced. However, the better- or worse-seeing eye at entry can be a confounding factor, and it cannot be discarded that the treatment effect will be the same in the better and worse seeing-eye. Secondarily, in order to verify this hypothesis, an adaptive randomization technique called Efron's minimization method will be used to minimize the imbalance of treatment groups between the better-seeing eyes treated and worse-seeing eyes treated.

Masking will be accomplished with sham injection of the fellow eye. Thus treatment allocation will be double-masked for both the subject and the investigation (follow-up) team. The pharmacy team, as well as the physician and medical team performing the GS010 administration and sham injection will be unmasked to treatment allocation. This treating, unmasked medical team will also perform the first follow-up visit (Visit 4), as well as focused follow up of ocular adverse events (AEs) commencing at Visits 3 and 4 until resolution of the AE or the determination that no further clinical evolution is expected. Centralized analysis of the Early Treatment Diabetic Retinopathy Study (ETDRS) visual acuity results, automated visual fields, SD-OCT, color vision and contrast sensitivity will be performed.

Trial visits:

The trial is divided into the following visits:

- Screening Visit (Visit 1): From 28 to 2 days before the investigational medicinal product (IMP) administration. This visit will allow Investigators to assess subject eligibility based on selection and non-selection criteria.
- Inclusion Visit (Visit 2): 1 day before the IMP administration.

This visit will allow Investigators to confirm the subject's eligibility based on inclusion and exclusion criteria. Subjects will undergo baseline ophthalmological testing.

After the subject is confirmed to be eligible for the study, the right eye will be randomized to GS010 or sham treatment based on a predefined central randomization scheme.

- Treatment Visit (Visit 3): Day of the IMP administration. Subjects will receive GS010 by IVT injection according to the randomized treatment assigned. The fellow eye will receive the alternative treatment.
- Follow-up visits (Visits 4 to 12): Nine follow-up visits after the IVT procedure will be conducted at 24 hours and 2, 4, 8, 12, 24, 48, 72, and 96 weeks.

The study plan is shown in Section 4.2.

A Data and Safety Monitoring Board meeting will be convened at least every 6 months to review the safety data.

Study duration:

Initiation of the trial with the first subject's first visit is planned for late Q4 2015. The estimated recruitment period is 12 months and will be dependent on recruitment rate. Total study follow-up is 96 weeks and the study will end with the last subject's last visit. The last subject's last visit is estimated to occur late Q4 2018. Therefore, the estimated study duration is 3 years.

At the end of this initial study period, a long-term safety and efficacy study as detailed in a future separate protocol will be initiated for further evaluation of the safety and efficacy durability. The long term safety study duration will be conducted according to current regulatory authority recommendation.

Primary Efficacy Endpoint:

The primary endpoint will be the ETDRS visual acuity (quantitative score) at Week 48 after IVT injection. The subjects' LogMAR scores, which are derived from the number of letters they read on the ETDRS chart, will be used for statistical analysis purposes. The change from baseline in each eye will be the primary response of interest.

Secondary Efficacy Endpoints:

- ETDRS visual acuity (quantitative score) over the follow-up period and at Week 96 after IVT injection. Change from baseline of the LogMAR scores will be used for statistical analysis purposes.
- Response status to treatment at Week 48 and 96 after IVT injection. Responder will be defined by an improvement of at least 15 letters in the visual acuity score obtained with ETDRS *or* being greater than a Snellen acuity equivalent of 20/200.
- Measure of parameters of high resolution SD-OCT of the posterior pole and optic nerve at Week 48 and Week 96.

- Measure of the standardized automated visual fields obtained with HVF Analyzer II. Mean Deviation (MD) in decibels of sensitivity will be used at Week 48 and Week 96.
- Measure of contrast sensitivity with the Pelli-Robson chart at Week 48 and Week 96.
- Measure of color vision with the Farnsworth-Munsell 100 Hue color vision test at Week 48 and Week 96.

Safety Endpoints:

• AEs and serious adverse events (SAEs), including those that are treatment-emergent and non-treatment-emergent, throughout the study period and at each study visit. Incidence and severity of systemic and local (ocular) AEs and SAEs will be determined at each clinical site and for the entire study cohort.

[figure not shown]

TABLE OF CONTENTS

Contents

Study	Summary	4
•	e of Contents	
List o	f Tables	12
List o	f Abbreviations	13
2 S	tudy Objectives	28
2.1	Primary	
2.2	Secondary	
	Secondary	
2.4	Safety	28
	tudy Endpoints	
3.1	Primary	
3.2	Secondary	
	Secondary	············
3.4	Safety	29
	tudy Plan	
4.1	Study Design	
4.2	Schedule of Events	32
4.2.1	Overall Schedule of Events	
4.2.2	Schedule of Events to be conducted by the Unmasked Site Team	
	opulation	
5 F 5.1	Number of Subjects	
5.2	Selection for the Study	
5.2 5.2.1	Selection Criteria	

qPCR quantitative polymerase chain reaction

rAAV2/2 recombinant adeno-associated viral vector, serotype 2

RGC retinal ganglion cell
RNFL retinal nerve fiber layer
SAE serious adverse event

SD-OCT spectral domain optical coherence tomography

SOP Standard Operating Procedure

SUN Standardization of Uveitis Nomenclature

TEAE Treatment-Emergent Adverse Event

WHO World Health Organization

[figure not shown]
2 STUDY OBJECTIVES

2.1 Primary

To evaluate the efficacy of GS010 compared with sham at Week 48 in the change from baseline of the Log of the minimal angle of resolution (LogMAR) in subjects affected for 6 months or less by LHON.

2.2 Secondary

- To evaluate the efficacy of GS010 compared with sham over the follow-up period and at Week 96 in the change from baseline of the LogMAR.
- To verify whether the efficacy at Week 48 and at Week 96 of GS010 compared with sham and measured by the change from baseline in the LogMAR is dependent upon the treatment of the better- or the worse-seeing eye.
- To verify whether the rate of responders at Week 48 and 96 is dependent upon the treatment received and whether the magnitude of the treatment effect is dependent the treatment of the better- or worse-seeing eye at entry.
- To assess the effect of GS010 on parameters measured with high resolution SD-OCT.
- To assess the effect of GS010 on visual fields obtained with the Humphrey Visual Field (HVF) Analyzer II.
- To assess the effect of GS010 on contrast sensitivity measured with the Pelli-Robson chart.
- To assess the effect of GS010 on color vision measure with the Farnsworth-Munsell 100 Hue color test.

3 STUDY ENDPOINTS

3.1 Primary

The primary endpoint will be the ETDRS visual acuity (quantitative score) at Week 48 after IVT injection. The subjects' LogMAR scores, which are derived from the number of letters they read on the ETDRS chart, will be used for statistical analysis purposes. The change from baseline in each eye will be the primary response of interest.

3.2 Secondary

- ETDRS visual acuity (quantitative score) over the follow-up period and at Week 96 after IVT injection. Change from baseline of the LogMAR scores will be used for statistical analysis purposes.
- Response status to treatment at Week 48 and 96 after IVT injection. Responder will be defined by an improvement of at least 15 letters in the visual acuity score obtained with ETDRS *or* being greater than a Snellen acuity equivalent of 20/200.
- Measure of parameters of high resolution SD-OCT of the posterior pole and optic nerve at Week 48 and Week 96.
- Measure of the standardized automated visual fields obtained with HVF Analyzer II. Mean Deviation (MD) in decibels of sensitivity will be used at Week 48 and Week 96.
- Measure of contrast sensitivity with the Pelli-Robson chart at Week 48 and Week 96.
- Measure of color vision with the Farnsworth-Munsell 100 Hue color vision test at Week 48 and Week 96.

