6.1.4.9 Visit 12 – Week 96 (or End of Study Visit)

The following procedures will be conducted at Week 96 (Visit 12, ± 30 days, or end of study visit) following IMP administration:

- ETDRS visual acuity testing performed prior to pupil dilation.
- Humphrey Visual Field 30-2 testing performed prior to pupil dilation.
- SD-OCT performed after pupil dilation.
- Pelli-Robson contrast sensitivity testing performed prior to pupil dilation.
- Farnsworth-Munsell 100 Hue color vision test performed prior to pupil dilation.
- Color fundus photos if necessary for grading ocular inflammation.
- Recording of AEs and SAEs.
- Recording of any changes and additions to concomitant medications and any changes in concomitant medication dose or regimen, including supplements.

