12.4.3 Analysis of Vision-Related Secondary Endpoints

SD-OCT will be presented by summary statistics for continuous data. Visual field data generated from HVF analyzer II, Goldmann applanation tonometry, color vision, and contrast sensitivity data will be summarized between the two treatments by using descriptive statistics.

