### **9.5.5 Secondary Variables**

#### GCL thickness/volume

The change of RGC layer thickness/volume from baseline to Week 48 will be based on ANCOVA including the subject and the eyes of the subject as random factors, the treatment, and the baseline GCL thickness/volume as covariates in the model. The analysis will be performed based on alpha of 0.05. The difference in the mean change from baseline (adjusted mean difference) to Week 48 between the two treatment groups (all-GS010 vs all-Sham and best-GS010 vs best-Sham) and associated 95% confidence interval will be reported.

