#### RNFL temporal quadrant and papillo macular bundle

The change of RNFL temporal quadrant and papillo macular bundle from baseline to Week 48 will be analyzed same way as GCL volume and topographical map

#### Change from baseline of the LogMAR scores at Week72/Week 96

The treatment estimate at Week 72/Week 96 will be based on the same statistical approach as the primary endpoint analysis for EMA between all-GS010 and all-Sham and Best-GS010 vs Best-Sham.

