### Parameters of High Resolution SD-OCT

A central reading center will perform quality control, analysis and interpretation of all SD-OCT data. The following parameters will be summarized:

- a. Retinal nerve fiber layer (RNFL) thickness
  - i. Total average (360 degrees)
  - ii. Temporal quadrant
  - iii. Papillomacular bundle (PMB)
  - iv. Nasal quadrant
  - v. Inferior quadrant
  - vi. Superior quadrant
- b. Central retinal/macula ETDRS area thickness, volume and topographical maps
  - i. Retinal Ganglion Cell (RGC) layer
  - ii. Inner Nuclear Layer
  - iii. Outer Nuclear Layer
  - iv. Total retinal thickness/volume

The parameter values and change from baseline at Week 48, Week 72 and Week 96 will be summarized by all-GS010 eyes and all-Sham eyes using summary statistics for continuous variables.

Mean graphs will be produced for all the parameters.

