### Measure of the standardized automated visual fields obtained with HVF Analyzer II.

Mean Deviation (MD) in decibels of sensitivity and Foveal threshold sensitivities at Week 48 , Week 72 and Week 96 and change from baseline to Week 48, Week 72, and Week 96 will be summarized by all-GS010 eyes and all-Sham eyes using summary statistics for continuous variables. The change of HVF parameters (Mean deviation and Fovea sensitivity) from baseline to Week48, Week 72 and Week 96 comparing All-GS010 vs All-Sham will be performed by using similar ANCOVA model mentioned for the primary analysis of LogMAR for EMA.

Forest plot will be presented displaying the magnitude of treatment effect and 95% confidence interval along with P-values. MMRM will be used to calculate the treatment effect and 95% confidence interval. A model similar to the one used for the time course of analysis for the LogMAR, will be used.

All the HVF parameter data will be listed.

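### SD-OCT at Week 96 is a named secondary endpoint, but the visible SAP models the GS010-versus-sham difference only at Week 48, leaving no planned paired, baseline-adjusted estimate or interval at Week 96

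*Protocol*

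**What the plan says.** **Protocol.** Section 3.2 names as a secondary endpoint "Measure of parameters of high resolution SD-OCT of the posterior pole and optic nerve at Week 48 and Week 96". The matching objective in section 2.2 is "To assess the effect of GS010 on parameters measured with high resolution SD-OCT", with no week attached. The data are collected at the last visit: the Visit 12 list in section 6.1.4.9 includes "SD-OCT performed after pupil dilation". For analysis, section 12.4.3 says only that "SD-OCT will be presented by summary statistics for continuous data", naming neither a model nor a visit.

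**SAP, Week 48.** Section 9.5.5 goes further than the protocol: "The change of RGC layer thickness/volume from baseline to Week 48 will be based on ANCOVA". Subject and eye are random factors, and treatment and the baseline OCT value are also in the model. The adjusted mean difference and its 95% interval are to be reported for all eyes and for best-seeing eyes. For the temporal RNFL quadrant, the change in it and in the "papillo macular bundle from baseline to Week 48 will be analyzed same way as GCL volume".

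**SAP, later visits.** The paragraph on SD-OCT parameters says: "The parameter values and change from baseline at Week 48, Week 72 and Week 96 will be summarized by all-GS010 eyes and all-Sham eyes". It adds mean graphs. SAP section 9 defines the summary of a continuous variable as number of observations, mean, SD, median, quartiles and range. That list contains no between-eye difference and no confidence interval.

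**SAP, other measures.** For visual field, the change to Weeks 48, 72 and 96 "comparing All-GS010 vs All-Sham will be performed by using similar ANCOVA model mentioned for the primary analysis of LogMAR for EMA".

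**The concern.** The endpoint covers two visits, but the modelled comparison covers only the first. A reader who wants the structural difference between GS010 and sham eyes at the end of follow-up will find two columns of group statistics. The design gives each subject one eye of each kind, so the natural contrast is within subject. Its standard error depends on the between-eye correlation, and two separate group SDs do not carry that information. The same SAP does provide a modelled contrast at this visit for the other continuous secondary measures and gives no reason for treating OCT differently.

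Timing adds to the concern. Protocol 12.6 unmasks the study for the Week 48 efficacy analysis, and Appendix V treats any analysis added after the code is broken as ad hoc. A Week 96 OCT model written after that point would be a choice made with the Week 48 OCT results available.

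**Working it through.** **Step 1. Is there a Week 96 OCT model elsewhere in the visible SAP?** Two sentences come close, and neither covers OCT. The sentence on Week 72/Week 96 estimates that follows the RNFL paragraph stands under its own heading, which concerns LogMAR change. The statement that the time-course analysis continues to Week 96 belongs to the LogMAR time course.

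**Step 2. Secondary measures at Week 96, side by side (SAP 9.5.5).**

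| Measure | Planned GS010-versus-sham comparison at Week 96 |
|---|---|
| LogMAR | ANCOVA as for the EMA primary analysis; repeated-measures time course |
| Visual field | ANCOVA; repeated-measures model |
| Contrast sensitivity | ANCOVA; repeated-measures model |
| Colour vision | Repeated-measures model, similar to the LogMAR time course that runs to Week 96 |
| Responder status | McNemar test (eyes), randomization test (subjects); no model |
| SD-OCT | None: summaries by all-GS010 and all-sham eyes, mean graphs |

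OCT is the only continuous measure in this list without a modelled contrast at Week 96. The later OCT summaries are also for all eyes only, so the best-eye contrast specified at Week 48 has no later counterpart.

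**Step 3. What the group summaries can and cannot give.** The documents state no figure for OCT. The number of pairs is taken from the sample-size section, which reproduces by the normal approximation: ((1.960 + 1.036)/0.50)² = 35.9, rounded up to 36.

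Let s be the per-eye SD of change, ρ the correlation between fellow eyes and N the number of pairs. Assume equal variances and complete pairs.

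- Paired standard error: s × √(2(1−ρ)/N)
- Unpaired standard error from group SDs: s × √(2/N)
- Ratio, unpaired to paired: 1/√(1−ρ)
- 95% half-width: the standard error times t with N−1 degrees of freedom (paired) or 2N−2 (unpaired)

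The documents give no ρ for OCT, so it is varied as an assumption, with N = 36:

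| ρ | SE ratio | Paired half-width (units of s) | Unpaired half-width (units of s) |
|---|---|---|---|
| 0 | 1.00 | 0.48 | 0.47 |
| 0.3 | 1.20 | 0.40 | 0.47 |
| 0.5 | 1.41 | 0.34 | 0.47 |
| 0.8 | 2.24 | 0.21 | 0.47 |

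Fewer pairs at Week 96 hardly changes the comparison: with N = 30 and ρ = 0.5 the half-widths are 0.37 paired and 0.52 unpaired.

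This calculation concerns the all-eye contrast. The best-eye contrast is between subjects, so pairing does not enter; what is missing there is the baseline-adjusted comparison. The ratios do not include any gain from the baseline covariate.

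**The case against.** The strongest reply is that the protocol never promised more. Its analysis section plans descriptive statistics for SD-OCT, and the SAP delivers them at Weeks 48, 72 and 96. The Week 48 model is an addition. This stands, and it rules out the inference that the SAP cut back a comparison the protocol had committed to.

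Four other strong readings are tempting and fail for similar reasons.

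- *The trial cannot meet its SD-OCT objective.* The objective names no week. The Week 48 model addresses it, and Week 96 is covered descriptively.
- *There is no estimate at Week 96.* With complete pairs, the difference between the two mean changes equals the mean paired difference. What is missing is a planned, adjusted estimate and a valid paired interval.
- *Baseline is ignored.* Change from baseline is summarised. Baseline is subtracted but not used as a covariate.
- *OCT is the only secondary endpoint without a modelled effect.* Responder status has tests only.

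It is also fair to say that the standard-error ratios describe a comparison a reader might improvise, not one the SAP plans, and that nothing is lost at ρ = 0. Finally, some text cannot be seen: SAP 4.2, the redacted blocks after the refraction paragraph, and the table shells. The visible OCT paragraphs read as complete, but the finding is limited to them.

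What survives is that the SAP chose to model OCT and stopped at the first of the two endpoint visits without a reason, while modelling the other continuous measures to the end.

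**Conclusion.** The point holds as an inconsistency among secondary endpoints. OCT at Week 96 is a named endpoint with data collected, and it has group summaries but no planned paired, baseline-adjusted GS010-versus-sham estimate or 95% interval. The cost in precision to a reader working from the summaries depends on an unknown between-eye correlation. The standard error is unchanged at ρ = 0, about 1.4 times the paired value at 0.5 and about 2.2 times at 0.8, given equal variances and complete pairs.

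The consequence is modest. SAP 9.5.3 makes every analysis other than the primary supportive, so the primary analysis, its error rate and the sample size are unaffected. The change is still worth making because the model already exists, the data are already planned, and the window to prespecify it closes at the Week 48 code break.

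**What to change.** Before the Week 48 code break, extend the two OCT model paragraphs in SAP 9.5.5 (GCL thickness/volume; RNFL temporal quadrant and papillomacular bundle) to change from baseline to Week 96. Report the adjusted mean difference and 95% interval and label them supportive. Week 72 is optional, since it is not part of the OCT endpoint. Keep the descriptive tables and mean graphs.

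If the sponsor prefers not to model OCT after Week 48, the SAP should say that those visits are descriptive only and why. If the code has already been broken, a Week 96 model can still be run but must be reported as ad hoc under Appendix V.

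The cost is SAP wording and extra model runs, with no new data. It also adds unadjusted comparisons. Three OCT measures, or four if RGC thickness and volume count separately, times two contrasts (all eyes, best eyes) gives 6 to 8 more at Week 96, or 12 to 16 if Week 72 is included. They should be read as estimates with intervals, not as confirmatory tests.
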